Don't Throw Your Heart Away: Clinician Study 3 Protocol

NCT04455893

Last IRB Check-In: Jan 10 2024

Study Information

Hypotheses

Hypothesis 1 When transplant centers present information on their transplant success rate only, evaluators will respond by selecting hospitals with higher transplant success. However, if information presented on transplant outcomes is stratified by the number and quality of donors used, or displayed in addition to total survival rates, then participants will respond by selecting hospitals with higher organ acceptance rates rather than the hospital with higher transplant outcomes. Thus, preference for the non-selective transplant center (relative to the selective center) will be lower in condition 1 (baseline: combined transplant survival only), compared to condition 2. That is, a higher proportion of participants will prefer the non-selective center over the selective center in condition 2, relative to condition 1. Hypothesis 2 The effect of information condition on choice will be mediated by ratings of the importance of getting a heart at all. That is, viewing information about stratified transplant survival will lead participants to think that the chance to "get a heart at all" is a more important factor in their decision which will in turn be associated with higher preference for the non-selective hospital. Specifically, ratings of importance (0-100 continuous scale) for the item "likelihood of getting any heart" will be lower in condition 1 than in condition 2. Furthermore, ratings on this item will be associated with choice, such that higher ratings will be associated with choice of the non-selective center. A bootstrapped mediation analysis will test for an indirect effect. Hypothesis 3 The difference in hospital preference between the treatment (stratified transplant survival) and control (combined transplant survival) conditions for the clinician participants will be smaller than the analogous difference observed in a previous study of layperson (Amazon Mechanical Turk) participants exposed to the same two conditions. In an analysis combining the data from the current study and the layperson study from the same two conditions in the previous study, we predict a 2 (information condition) x 2 (participant population) interaction, such that that effect of information condition is smaller for expert clinicians than for lay people.

Design Plan

Study type

Experiment - A researcher randomly assigns treatments to study subjects, this includes field or lab experiments. This is also known as an intervention experiment and includes randomized controlled trials.

Blinding

- For studies that involve human subjects, they will not know the treatment group to which they have been assigned.

Is there any additional blinding in this study?

n/a

Study design

We have a between-subjects design in which participants are randomized to one of two information conditions (independent variable). In each condition, they make a choice (dependent variable) between two hospitals (one with a non-selective donor acceptance strategy, and another with a more selective donor acceptance strategy). Independent variables: (1) Condition 1 ("baseline" condition): view only combined transplant survival (e.g. transplant

survival rate not stratified by number and quality of donor hearts accepted at each center) (2) Condition 2: view only stratified transplant survival (e.g. transplant survival rate stratified into patients who received excellent donor organs and patients who received less than optimal donor organs) These two conditions will be analyzed for our primary analysis: a 1x2 design with 2 arms (control arm or combined transplant survival, and experimental arm or stratified transplant survival).

Randomization

We will use simple randomization, where each participant will be randomly assigned to one of the two predetermined conditions. The Qualtrics randomizer function will be used for randomization into a condition.

Sampling Plan

Existing Data

Registration prior to creation of data

Explanation of existing data

n/a

Data collection procedures

125 transplant clinical personnel participants will be recruited from the International Society for Heart and Lung Transplantation (ISHLT) and the Pediatric Heart Transplant Society (PHTS). Participants will be recruited via (1) the ISHLTConnect Discussion Board webpage, (2) the PHTS Basecamp Discussion Board webpage and corresponding Listserv, and (3) the PHTS July 2020 Live Webinar (via Zoom). Inclusion criteria: Participants who are transplant clinical personnel will be asked to participate if they confirm the following inclusion criteria in the consent form. (1) 18 years of age or older (2) must read and understand the information in the consent form (3) must want to participate in the research and continue with the survey Payment: Participants will be given the option to select a transplant-related charity at the end of the survey that will receive a \$1.50 donation (anonymously) if they complete the survey.

Sample size

Our target sample size is 122 participants. We expect that this will amount to approximately 61 participants per condition, although due to the nature of the randomization technique used (Qualtrics randomizer function), we may end up with slightly more or slightly less than 61 per condition.

Sample size rationale

A sample size of 61 per group was calculated to yield at least 90% power to detect a 30 percentage point difference between conditions (e.g., 35% vs. 65%) with $\alpha=0.05$ (GPower 3.1.9.4).

Stopping rule

We will stop data collection after the first of the following three scenarios is achieved: (1) 122 responses collected (2) August 31, 2020 and at least 100 responses collected (3) October 31, 2020.

Variables

Manipulated variables

We will manipulate how transplant center outcomes are presented. Different components of the same outcome statistics for two transplant centers will be varied over two different conditions. (1) Condition 1 ("combined" condition): view only combined transplant survival (e.g. transplant survival rate not stratified by number and quality of donor hearts accepted at each center) (2) Condition 2 ("stratified" condition): view only stratified transplant survival (e.g. transplant survival rate stratified into patients who received excellent donor organs and patients who received less than optimal donor organs) The two conditions will be included in our main analysis, which is a 2x1 design with 1 factors (transplant survival) and 2 levels per factor: "combined": reference level, in which transplant survival rate is not stratified by number and quality of donor hearts accepted at each center "stratified": transplant survival rate stratified into patients who received excellent donor organs and patients who received less than optimal donor organs

Measured variables

The outcome variable will be a binary choice between two hospitals: one with a selective donor-heart acceptance strategy and one with a non-selective donor heart acceptance strategy. Participants will respond to the question "Which Hospital do you consider to be higher performing? Please click on one of the two tables below to indicate which hospital is the better choice." Participants will choose between two outcome tables featuring the selective and non-selective hospital (counterbalanced, such that each of the two choices is equally likely to be presented at top of the choice scenario in each condition). The number of participants that choose each hospital will be the measured outcome variable used in analyses. On the next page of the survey, participants will respond to three mediator questions: "There are many reasons why one transplant hospital might outperform another. Which reasons were most important in your decision? Please move the slider to indicate how much you considered each of the reasons below (0=reason was not important, 100=reason was extremely important)." Participants will then move a slider bar (0-100) to indicate the importance of the following three items: (1) Patients were more likely to receive an excellent donor heart at the hospital I picked. (2) Patients were less likely to receive a marginal donor heart at the hospital I picked. (3) Patients were more likely to receive any kind of heart at the hospital I picked. The third item (more likely to receive any kind of heart) will be the only variable that is included in the planned mediation analysis.

Indices

n//a

No files selected

Analysis Plan

Statistical models

To test Hypotheses 1, we will use a binomial logistic regression analysis. The categorical independent variable will be 'stratified transplant survival'; the dependent variable is binary choice of hospital. -We will test whether the main effect of "stratified transplant survival" is statistically significant and in the predicted positive direction. To test Hypothesis 2, we will conduct a causal mediation analysis to determine whether information display had a mechanistic effect on hospital choice through our proposed mediator. We will estimate the average causal mediation effect (ACME), average direct effect (ADE), and the total effect. The ACME is the effect of the experimental information display condition (stratified) on the outcome of hospital choice (selective vs. non-selective), mediated through the hypothesized mediator (the importance of "getting any heart" at each hospital when considering the choice). The remaining effect of information display on hospital choice that is not mediated through the hypothesized mediator represents the ADE. The entire effect of the information display on hospital choice via the hypothesized mediator and the direct effect is the total effect. The proportion of the total effect that is accounted for by the ACME is called the proportion mediated.{Imai, 2010}. Analyses will be performed using the "mediation" package in R (The R Foundation for Statistical Computing).{Tingley, 2014}. We will generate 95% confidence intervals by using 1000 bootstrap simulations. The unstandardized point estimate of the ACME and its 95% confidence intervals will be interpreted. -A significant ACME for "stratified transplant survival" would suggest that stratifying transplant survival by number and quality of accepted donors works via increasing the perceived importance of "getting any heart" to increase preference for the non-selective hospital. If the ACME is non-significant, we will identify where the causal path breaks down. To test Hypothesis 3, we will conduct an analysis combining the data from the current study and the layperson study from the same two conditions in the previous study. We predict a 2 (information condition) x 2 (participant population) interaction, such that that effect of information condition is smaller for expert clinicians than for laypeople.

No files selected

Transformations

Logistic regression analysis: The categorical predictor "transplant survival stratified" will be dummy coded (0=not stratified, 1=stratified), with 'stratified' as the reference category. The outcome variable "choice of hospital" will be dummy-coded (0=selective hospital, 1=non-selective hospital). The reference category is 'selective hospital'. Mediation analysis: The categorical predictor "transplant survival stratified" will be dummy coded (0=not stratified, 1=stratified), with 'stratified' as the reference category. The continuous mediator variable "get any heart" will be mean-centered for each analysis. The outcome variable "choice of hospital" will be dummy-coded (0=selective hospital, 1=non-selective hospital). The reference category is 'selective hospital'.

Inference criteria

We will use the standard $p=0.05$ criteria for determining if the results are significantly different from those expected if the null hypothesis were correct.

Data exclusion

n/a

Missing data

If a participant does not complete the entire survey, they will not be included in the analysis.

Exploratory analysis

No response

Other

Other

No response

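### Does Hypothesis 3 need its own sample-size or precision statement, given that 61 per arm was chosen for the two-arm contrast alone?

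*Combined protocol and SAP*

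**What the plan says.** Hypothesis 3 (Hypotheses section) is directional: "The difference in hospital preference between the treatment (stratified transplant survival) and control (combined transplant survival) conditions for the clinician participants will be smaller", measured against the corresponding difference in an earlier layperson study. Statistical models gives the test: "To test Hypothesis 3, we will conduct an analysis combining the data from the current study and the layperson study", with the expected result put as "We predict a 2 (information condition) x 2 (participant population) interaction". It names no effect scale, model or sidedness for this hypothesis.

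Sample size rationale contains the only power statement: "A sample size of 61 per group was calculated to yield at least 90% power to detect a 30 percentage point difference between conditions", with 35% against 65% as the example. Study design says which contrast that serves: "These two conditions will be analyzed for our primary analysis: a 1x2 design with 2 arms". The Stopping rule lets recruitment end early, one route being "August 31, 2020 and at least 100 responses collected". Inference criteria sets 0.05 as the "criteria for determining if the results are significantly different from those expected if the null hypothesis were correct" and exempts no hypothesis.

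For Hypothesis 2 the plan says what follows a null result: "If the ACME is non-significant, we will identify where the causal path breaks down". It has no matching sentence for Hypothesis 3.

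**The concern.** An interaction between condition and population is a difference of two differences, so it carries the sampling error of both studies. A sample that is comfortable for one 30-point difference can be too small to show that this difference is smaller than another one. There is also a tension between hypotheses. The same 122 clinicians are expected to show an effect (Hypothesis 1) and a smaller effect than laypeople (Hypothesis 3), and the smaller the clinician effect, the easier the second becomes and the harder the first.

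What would be at stake is interpretation. A non-significant interaction might be reported as clinicians responding like laypeople, which a wide interval cannot support.

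**Working it through.** **Inputs from the plan:** 61 clinicians per arm, 35% and 65%, alpha 0.05 (Sample size and Sample size rationale).

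**Assumptions, because the documents are silent:** two-sided test, 80% power as the yardstick for Hypothesis 3, and layperson rates and numbers as stated in each line.

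**1. The plan's own figure.** Exact power of the two-sided Fisher test for 35% against 65% is 0.892 at 60 per arm and 0.901 at 61. So 61 is the first size to reach 90%, and the stated figure reproduces.

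**2. Best case for Hypothesis 3: clinicians at 35% to 65%, layperson effect known without error.**

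- Risk difference: SE = sqrt(2 × 0.2275/61) = 0.0864. Required gap = (1.960 + 0.842) × 0.0864 = 0.242. Layperson shift = 0.300 + 0.242 = 0.542, about 54 points.
- Log odds: the clinician odds ratio is (0.65/0.35)² = 3.449, with log 1.238. SE = sqrt(2/(61 × 0.2275)) = 0.380. Required layperson log odds ratio = 1.238 + 2.802 × 0.380 = 2.302, an odds ratio of about 10.
- In points, an odds ratio of 10 depends on the layperson baseline. It is 51.9 if rates are symmetric about 50% (24% to 76%), which is the largest value. It is 49.3 from a 35% baseline, 42.6 from 10% and 29.5 from 5%. On this scale there is no fixed floor in points.
- A one-sided 0.05 test lowers the figures to 51.5 points (risk difference) and 49.7 points (log odds, symmetric rates).

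**3. Power at other true effects.** Power ≈ Φ(gap/SE − 1.960). For 20 against 50 points with 100 laypeople per arm (clinicians 40% to 60%, laypeople 25% to 75%): SE = sqrt(2 × 0.24/61 + 2 × 0.1875/100) = 0.108, and 0.30/0.108 gives power of about 0.80. Other cases, rates symmetric about 50%, from formula or simulation:

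| Clinician vs layperson shift | 100 laypeople per arm | 400 per arm |
|---|---|---|
| 15 vs 30 points | 27% | 35% to 37% |
| 20 vs 40 | 45% | 56% to 60% |
| 30 vs 40 | 15% | 18% to 21% |
| 10 vs 40 | 77% to 78% | 88% to 91% |
| 20 vs 50 | 80% | 89% to 93% |
| 30 vs 60 | 83% to 84% | 91% to 96% |

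Ranges cover the two scales and the two methods.

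**4. Dependence on scale.** With rates near 50% the two scales agree closely. Away from it they do not. With a shared 10% baseline, 20 against 40 points and an effectively unlimited layperson sample, power is about 81% for the risk difference and 38% (formula) to 43% (simulation) for log odds. With laypeople at 35% to 65% and clinicians at 10% to 25%, it is 26% to 61% against 4% to 6%.

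**5. Early stopping.** At 50 clinicians per arm with 100 laypeople per arm, 20 against 40 points falls from 45% to 40%, a small loss.

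**6. What more clinicians would cost.** For 80% power at 20 against 40 points, 84 to 95 per arm are needed with unlimited laypeople and 111 to 119 with 400 per arm. With 100 laypeople per arm, the total variance allowed on the risk-difference scale is (0.20/2.802)² = 0.00510, of which laypeople use 2 × 0.21/100 = 0.0042. That leaves 0.0009, so about 536 clinicians per arm.

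**The case for a change.** The strongest case for acting is that Hypothesis 3 is numbered, directional and tested at 0.05, while a true halving of a 30- or 40-point layperson effect would often be missed: power is 27% or 45% in the table above with 100 laypeople per arm. Significance on both Hypotheses 1 and 3 would be rare in those cases, at most 1.6% at 15 against 30 points and 11% to 27% at 20 against 40 (symmetric rates). The layperson data already exist, so stating the detectable interaction, naming a scale and adding a sentence about null results would cost almost nothing.

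The arithmetic stands, for mid-range rates and the effects chosen. It does not show a fault in the plan. Sizing a study on its primary contrast and accepting whatever precision results for other hypotheses is ordinary practice. The plan does not require Hypotheses 1 and 3 to succeed together, so joint power tests a criterion it never sets. Nor does it say that a null interaction will be read as equal effects. The 30-point clinician shift is the design value for Hypothesis 1, not a prediction for Hypothesis 3, and with a smaller clinician shift the test can be adequate.

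The unstated scale is a real gap, since the choice can change the answer when baselines are low or unequal. But the natural reading extends the logistic regression of Hypothesis 1 with a product term. The outcome is binary, so reporting the four cell counts lets any reader compute either scale.

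**Conclusion.** No change is called for. The power claim in the plan belongs to the two-arm contrast, and 61 per group meets it. Hypothesis 3 has no stated power to fall short of. Its precision may be poor: about 54 points, or an odds ratio of about 10, would be needed in laypeople if clinicians shift from 35% to 65% (two-sided 0.05, 80% power, unlimited laypeople). But the layperson counts are not in the documents, and depending on them and on the true clinician effect the test may be weak or sound.

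What is missing is detail that an analyst fills sensibly: the scale, an interval for the interaction, and the usual caution that non-significance does not show equality. Replacing the test by estimation would trade away the directional verdict the investigators want. A larger clinician sample would serve a non-primary question, at a cost running from 84 to more than 500 per arm for 20 against 40 points. The conclusion rests on Hypothesis 3 being secondary to the two-arm comparison, as Study design indicates.

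### Does a stopping rule that allows fewer than 122 responses undercut the stated 90% power?

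*Combined protocol and SAP*

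**What the plan says.** All references are to the combined protocol and SAP.

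- **Sample size:** "Our target sample size is 122 participants", expected to fall about equally into the two arms, 61 in each.
- **Sample size rationale:** the only power claim is "A sample size of 61 per group was calculated to yield at least 90% power to detect a 30 percentage point difference between conditions", with 35% against 65% as the example, "with $\alpha=0.05$ (GPower 3.1.9.4"). Whether the test is one- or two-sided is not stated.
- **Stopping rule:** collection ends at the first of three events. The first is 122 responses. The other two read "August 31, 2020 and at least 100 responses collected (3) October 31, 2020".
- **Data collection procedures:** "125 transplant clinical personnel participants will be recruited".
- **Randomization:** "We will use simple randomization, where each participant will be randomly assigned to one of the two predetermined conditions".
- **Statistical models:** "To test Hypotheses 1, we will use a binomial logistic regression analysis".
- **Missing data:** "If a participant does not complete the entire survey, they will not be included in the analysis".

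**The concern.** Only one power figure is given, and it belongs to the largest of the permitted samples. Two of the three stopping events allow fewer than 122 responses. The third has no floor. Read literally, the second event ends collection as soon as 100 is reached on or after August 31, so the October 31 stop can govern only when fewer than 100 responses are in hand.

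Two smaller points add to the doubt. The Stopping rule counts responses without defining them, while unfinished surveys are left out of the analysis, so even a stop at 122 might leave fewer than 122 analysed. The text also gives both 125 and 122 without relating them.

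If this mattered, a non-significant Hypothesis 1 result after an early stop would be read against a sensitivity of 90% or more that the study did not have.

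**Working it through.** **Inputs.** From the Sample size rationale: p1 = 0.35, p2 = 0.65, difference 0.30, alpha 0.05, n = 61 per group. From the Stopping rule: 122, 100 and no minimum. A two-sided test is assumed.

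**1. The plan's own figure.** Pooled z test with equal groups:

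power = Φ{[0.30·√n − 1.96·√(2·0.5·0.5)] / √(0.35·0.65 + 0.65·0.35)}

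The two constants are 1.96·√0.5 = 1.386 and √0.455 = 0.6745.

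- n = 61: (2.343 − 1.386)/0.6745 = 1.419, power **92.2%**.
- Other methods at 61 per group: arcsine 92.0%; exact enumeration of the logistic Wald test 92.9%; Fisher's exact test 90.1%.

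Every method gives at least 90%, so the stated figure reproduces.

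**2. Smallest sample that keeps 90% (z test).** n = [(1.386 + 1.2816·0.6745)/0.30]² = (2.250/0.30)² = 56.3, so 57 per group, or 114 in total.

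**3. The permitted stops.** By the same formula:

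- n = 50 (100 in total): (2.121 − 1.386)/0.6745 = 1.090, power **86.2%**.
- n = 40 (80 in total, an illustration only): (1.897 − 1.386)/0.6745 = 0.758, power **77.6%**.

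The table uses the planned logistic Wald test, and Fisher's test for comparison. Both are enumerated exactly and averaged over the group sizes that simple randomization produces.

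| Total analysed | Wald | Fisher |
|---|---|---|
| 122 | 92.0% | 91.0% |
| 114 | 90.0% | 87.6% |
| 100 | 86.1% | 84.2% |
| 80 (illustration) | 77.5% | 74.3% |

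With exactly 50 per group, Fisher gives 82.8%. On the planned Wald test, an August 31 stop with 114 to 121 analysed keeps about 90% or more. The shortfall there is confined to 100 to 113.

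**4. Dependence on the example and on sidedness.** The pair 35/65 is the 30-point pair with the largest variance. At 50 per group (z test), 20% against 50% gives 89.4% and 10% against 40% gives 94.6%. A one-sided 0.05 test of 35% against 65% at 50 per group would give 92.2%. The documents do not say the test is one-sided, and two-sided is the natural reading.

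**5. Unfinished surveys.** No rate is given. If unfinished surveys counted toward 122, the Wald margin would be 122 − 114 = 8 of them, about 7%. For assumed rates of 5%, 10% and 20%, z power from 122 responses would be 90.8%, 89.3% and 85.4%. If responses means completed surveys, the loss is zero.

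**6. Precision.** The 95% half-width for the difference is 1.96·√(2·0.2275/n): 16.9 points at 61 per group and 18.7 at 50. The interval widens by under 2 points.

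**The case for a change.** The best case for a change is that the plan names 35% against 65% itself, and that for this pair two of its three stopping events can end below the only power it states. The chance of missing the effect rises from 8.0% at 122 (100 − 92.0) to 13.9% at 100 (100 − 86.1) and 22.5% at an illustrative 80 (100 − 77.5). Whenever the October 31 date is what ends collection, fewer than 100 responses are in hand; even 99 analysed gives only 85.1% by averaged Wald. A few words would put this on record at no cost in recruitment.

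The arithmetic stands, and so does the observation that the October 31 stop has no floor. The inference that the plan misstates its power does not. The power sentence is tied to 61 per group and is true there, and a reader meets the stopping rule in the next section. The calendar limits are a prespecified feasibility rule for a volunteer survey of society members, a fair trade between size and time.

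The side points carry little weight. The Sample size section equates 122 with about 61 participants per condition, the number in the power sentence, which favours reading responses as usable surveys. Recruiting 125 to obtain 122 is a plausible small allowance, and the difference has no bearing on the test. Reporting a detectable difference after the data are in would add little to the confidence interval for the estimated effect.

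**Conclusion.** No change is needed. The sample size calculation has no error. What remains is missing detail: power at the smaller permitted samples is not written down. At 100 analysed it is about 86% by the planned logistic test, about 4 points under 90%. That figure assumes a two-sided 0.05 test, true rates of 35% and 65%, and 100 analysable surveys. Under an October 31 stop it is lower, by an amount that depends on a count the plan does not fix.

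Because stopping depends on the calendar and the number of responses, never on which hospital participants chose, the Hypothesis 1 test keeps its type I error and its estimate is not biased by the rule. A smaller sample would show in a wider interval and in the reported number analysed. An analyst following the plan as written would count completed surveys, report how many were analysed, and reach the same Hypothesis 1 conclusion whether or not extra power figures had been stated.

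### Display position of the hospital tables is a counterbalanced design factor but is not in the H1 model; prespecifying it would be a cheap, optional improvement

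*Combined protocol and SAP*

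**What the plan says.** The Measured variables section of the combined protocol and SAP describes the outcome as a click on one of two hospital tables, with their order "counterbalanced, such that each of the two choices is equally likely to be presented at top of the choice scenario in each condition". Statistical models opens with "To test Hypotheses 1, we will use a binomial logistic regression analysis" and continues: "The categorical independent variable will be 'stratified transplant survival'; the dependent variable is binary choice of hospital". Transformations codes one dummy predictor, the condition, and no position variable. Manipulated variables describes the main analysis as "a 2x1 design with 1 factors (transplant survival) and 2 levels per factor".

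Position does not appear anywhere as a covariate, a stratum or a sensitivity analysis, and Exploratory analysis is left without a response. Simple randomisation through the survey platform is specified under Randomization for the information condition; how the table order is assigned is not described. On size, Sample size rationale states "A sample size of 61 per group was calculated to yield at least 90% power" for 35% against 65%. The Stopping rule allows closure from August 31, 2020 with 100 responses.

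**The concern.** A factor that the design controls because it could affect the outcome would normally also be in the analysis. Here the outcome is which of two stacked tables is clicked, so an order effect is plausible.

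If position affects choice, two things follow. Under independent assignment of position, the arms can differ by chance in the share who saw the non-selective table on top, and the one-predictor model leaves that difference in the estimate. Under enforced equal counts there is almost no imbalance, but the unadjusted test counts position-related variation as noise that the design has already removed. In either case some power for H1 may be lost, and this matters more if the study closes near 100 responses. A further point is that, without a prespecified choice, an imbalance seen later invites a post hoc decision between adjusted and unadjusted results.

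**Working it through.** **Inputs from the documents.** 61 per arm; 35% vs 65%; alpha 0.05 (two-sided assumed, since it reproduces the stated size); possible closure at 100 responses. **Assumed.** The position effect, expressed as an OR. At these choice rates, ORs of 2, 3 and 4 correspond to about 16, 24 and 30 percentage points.

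**1. The plan's own figure.** Exact power of a two-sided Fisher test is the sum of Bin(i; n, 0.35) × Bin(j; n, 0.65) over all tables with p ≤ 0.05. This gives 89.24% at 60 per arm and 90.07% at 61. The stated 61 reproduces, and the absence of position does not make it wrong.

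**2. Chance imbalance under independent draws.** SD of the between-arm difference in position share = √(0.25 × 2/n). For n=61 this is 9.1 points; for n=50 it is 10.0 points. A difference above 15 points is 15/9.1 = 1.66 SD (about 10% of trials) or 15/10 = 1.5 SD (about 13%). In simulation the arm difference moved by 0.23 to 0.25 points per point of imbalance at OR 3, and by 0.29 to 0.31 at OR 4. A 15-point imbalance therefore shifts it by 15 × 0.23 = 3.5 to 15 × 0.31 = 4.7 points.

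**3. Power under independent draws.** Logistic models with and without position, 20,000 trials per cell, marginal rates held at 35%/65%:

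| Position OR | N=122 unadjusted | N=122 adjusted | Change |
|---|---|---|---|
| 1 | 92.6% | 92.3% | −0.3 |
| 1.5 | 92.4% | 92.3% | −0.1 |
| 2 | 92.2% | 92.6% | +0.4 |
| 3 | 92.6% | 93.8% | +1.2 |
| 4 | 92.5% | 94.5% | +2.0 |

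The Monte Carlo standard error of each power is √(0.925 × 0.075/20,000) = 0.19 points. Repeat runs at N=122 gave +0.2 to +0.4 at OR 2, +1.2 to +1.3 at OR 3 and +1.9 to +2.0 at OR 4. At N=100 one run gave 86.5/86.1 (OR 1), 86.7/87.2 (OR 2), 86.3/88.3 (OR 3) and 86.6/89.8 (OR 4). Across runs the N=100 gains were about 0.5 to 0.6, 1.5 to 2.0 and 2.8 to 3.2 points at ORs 2, 3 and 4.

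A separate run of 8,000 trials with exactly 61 per arm put break-even higher: 93.0 vs 92.6 at a 10-point effect, which is OR (0.55/0.45)² = 1.5, and 93.1 vs 93.2 at 20 points, which is OR (0.60/0.40)² = 2.25. In that run, with no position effect, the unadjusted test had type I error 5.9% against 5.5% adjusted, so part of the apparent cost may reflect test size.

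**4. Enforced balance.** Per-person variance relevant to the arm difference falls from p(1−p) to p(1−p) − (d/2)², where d is the position effect, but the unadjusted test still uses p(1−p). With both arms at 50% and OR 3, d = 0.268 and (0.134)²/0.25 = 0.072. The effective critical value is 1.96/√0.928 = 2.03, a true level of about 4.2%. At OR 4, d = 0.333, the ratio is 0.111, the critical value is 2.08 and the level is about 3.8%. Simulation gave 4.1% to 4.6% over ORs 3 and 4 unadjusted, and 4.9% to 5.4% adjusted. Power was 93.1/93.9 at OR 3 and 93.5/94.6 at OR 4. With 10- and 20-point effects it was the same with and without the term (92.8% and 93.6%).

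**The case against.** Counterbalancing is itself the control for position. The randomised comparison is unbiased on average without the covariate. Unadjusted type I error under independent draws was 5.3% to 6.0%, against 5.1% to 5.5% adjusted, so adjustment does not repair a faulty test. The material gains need a position effect of 24 to 30 points, which rivals the 30-point effect the study is powered for, and nothing in the documents suggests one that large. A prognostic covariate also does not shrink the standard error of a log odds ratio: the estimate becomes a conditional odds ratio, and any gain is in power. All of this stands, and it limits the point to an optional refinement.

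A reader might infer more: that the primary analysis is biased, that the arms are bound to be imbalanced on position, or that adjustment gives free precision. The documents support none of these. They do not say that order is drawn independently for each participant, so imbalance is possible but not certain. With no position effect, adjustment costs about 0.3 points of power. The lower power at 100 responses comes from the stopping rule and not from the missing term.

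What the objection does not remove is that the factor is already assigned, the term is one variable, and under either reading of counterbalancing it helps if position matters materially.

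**Conclusion.** The point holds as a low-priority improvement. Position is a controlled design factor that the H1 model omits; the planned test is valid as written. At N=122 with independent draws, the change in power runs from about −0.3 points (no position effect) to about +2.0 (OR 4), with break-even between ORs of about 1.5 and 2.25 depending on the run. At N=100 the gain reaches about 3 points at OR 4. With enforced balance, adjustment restores the nominal level of a mildly conservative test and cost no power at the ORs tested. These sizes rest on 35% vs 65%, a two-sided test, no interaction between position and condition, and assumed position effects. The larger gains should not be expected without evidence of a strong order effect.

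**What to change.** - In Measured variables, state how the order is assigned: independent draws or enforced equal counts within condition.
- In Statistical models, define H1 as choice (1 = non-selective) on information condition plus display position (non-selective table on top, yes/no). Test the condition coefficient as now planned.
- Report the arm difference in percentage points standardised over position, because the adjusted odds ratio is conditional.
- If position is used in H2, put it in both the mediator and the outcome model, since the importance items ask about the hospital the participant picked.
- Leave H3 unadjusted unless display order is also available in the layperson data; the documents do not show that it is.
- Export the display-order field, and keep the unadjusted H1 model as a sensitivity analysis.

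The cost is a short change to the analysis plan, one exported field, one degree of freedom, and about 0.3 points of power if position has no effect.
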